Body weight	X	X	Х	Х	Х	Х	Х	Х	X	X	Attention should be given to weigh the participant on the same scale through the duration of the study. Participants should be weighed wearing underwear and a gown; participants will be instructed to take off their shoes and to empty their bladders before being weighed. Note: if disrobing for weighing is logistically impossible, the participant must be dressed as lightly as possible, with consistency from visit to visit
Waist Circumference Measurement	X	X	Х	X	X	X	Х	Х	Х		Measured with the participant standing, wearing underwear, with or without a gown. The measurement will be performed at a level midway between the superior aspect of the iliac crests and the lower lateral margin of the ribs. The measurement need not be at the level of the umbilicus. The measuring tape will be kept horizontal.
Body Composition via DEXA scan		X			X			Х	Х		Performed between screening and baseline (+2 weeks), at Weeks 24, 48, and the ESID visit (±10 days) (only to be performed at ESID if the last scan is more than 12 weeks from the date of the ESID visit and the ESID visit takes place before Week 48). A rescan for technical reasons at all scheduled time points is allowed within 2 weeks.
Complete physical examination	X	X						X	X		
Symptom-directed physical examination			X	X	X	X	X			X	May be conducted at all other scheduled/unscheduled study visits based on reported safety or tolerability issues.
Concomitant medications	X	X	X	X	X	X	X	X	X	X	

Phase	Screeninga	Baseline		48-W	eeks Tre	atment P	hase ^c	ESIDe	30-Day FU ^f	Remarks	
Visit		Day 1 ^b	Week 4	Week 12	Week 24	Week 28 ^d	Week 36	Week 48			
Study Procedures											
Adverse events (AEs)	X	X	X	X	X	X	X	X	X	X	In the setting of a suspected renal AE, serum creatinine and urine chemistry will be assessed (creatinine, sodium, phosphate, glucose, protein, albumin).
Fasting Clinical Laboratory Tests											
Chemistry profile	X	X	X	X	X	X	X	X	X	X	
Metabolic profile		X			X			X	X		If a participant has not fasted prior to the visit, the visit may proceed, but participant must return within 72 hours in a fasted state to have a blood draw.
Leptin and Adiponectin		X			X			X	X		
Alpha Melanocyte-Stimulating Hormone		X			X			X	X		
Hematology profile	X	X	X	X	X	X	X	X	X	X	
eGFRcr	X	X	X	X	X	X	X	X	X	X	eGFRcr by Cockcroft Gault
Urinalysis	X	X	X	X	X	X	X	X	X	X	Dipstick. If dipstick results are abnormal, the sediment will be examined microscopically.

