2.2. Visit Windows

As subjects do not always adhere to the protocol visit schedule, the following rules are applied to assign actual visits to analysis visits. Listed below are the visit windows and the target days for each visit. The reference day is Study Day 1. If a subject has 2 or more actual visits in one visit window, the visit closest to the target day will be used as the protocol visit for that visit window. The other additional visit(s) will not be used in the summaries or analyses, but they can be used for determination of clinically important endpoints. If 2 actual visits are equidistant from the target day within a visit window, the later visit is used.

All assignments will be made in chronological order. Once a visit date is assigned to a visit window, it will no longer be used for a later time point except for the endpoint. Listed below (Table 2) are the analysis time points (week), visit windows and the target days for each visit defined in the protocol during the treatment phase. The time intervals will be used for reporting of metabolic/weight, efficacy, and safety data.

Table 2. Visit Windows

	Immediate Switch Arm - Time	Delayed Switch Arm - Time	
Analysis	Interval	Interval	Target Time
Time Point a	(Day)	(Day)	Point (Day)
Screening	Day-42 - <day 0<="" td="">Day-42 - <day 0<="" td="">-∞	</day>	</day>	Day-42 - <day 0<="" td="">-∞	</day>	-∞
Baseline b	≤Day 1	≤Day 1	1
Week 4	Day 2 – Day 56	Day 2 – Day 56	29
Week 12	Day 57 – Day 126	Day 57 – Day 126	85
Week 24	Day 127 – Day 210	Day 127 – Day 182	169
Week 28	NA	Day 183 – Day 224	197
Week 36	Day 211 – Day 294	Day 225 – Day 294	253
Week 48	Day 295 – Day 378	Day 295 – Day 378	337

^a For subjects discontinuing treatment early, data collected at that visit will count towards the time interval based on days relative to baseline.

Note: Target Time Point (Day)=Week $x\times7 +1$; Time Interval (Day), for example, Start day=127=(85+169)/2 and then obtain the previous interval End day=127-1=126. Similarly, for other intervals' Start day and End day.

Phases will be constructed for each subject as follows for adverse events, concomitant therapies, and for the determination of the worst-case/toxicity/change in the cross-tabulations.

^b The baseline visit (Day 1) cannot proceed until the investigator has received all results of the screening visit and participant eligibility has been confirmed.

Trial phase	Start date	End date

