Screening	Minimum of date of signing the informed consent and date of the screening visit, no early than Day -42	1 day before start of treatment or day 1 of treatment whichever the last before first dose.
Treatment	Date of the first intake (after	For ongoing/completed subjects, in order of priority:
Phase I	randomization)	 For delayed switched arm, use first D/C/F/TAF intake date – 1;
		- For immediate switch arm, use Week 24 visit date; if missing then
		 Projected Week 24 visit date
		Projected Week 24 visit date = first dose date $+ (7 \times 24)$.
		In case of withdrawal before Week 24 visit : Date of last intake +7 days. If the last dose date is missing, use the following date in order of priority:
		- The date of treatment termination + 7 days;
		- The first available follow-up visit date-1 day;
		- The earlier of projected Week 24 visit date +7 and Trial discontinuation date + 7, where projected Week 24 visit date = first dose date + (7×24).
Treatment	Treatment Phase I end date +1	For ongoing/completed subjects, in order of priority:
Phase II	day	- Week 48 visit date + 7; if missing then
		 Projected Week 48 visit date +7, where projected Week 48 visit date = first dose date + (7×48).
		In case of withdrawal after Week 24 visit: Date of last intake +7 days. If the last intake date is missing, use the following date in order of priority:
		- The date of withdrawal + 7 days;
		- The first available follow-up visit date-1 day;
		- The earlier of projected Week 48 visit date +7 and trial discontinuation date + 7, where projected Week 48 visit date = first dose date + (7×48).
*Follow-up	End of the last treatment phase +1 day	Trial termination date for all groups (date of last contact)

⁺¹ day contact)

*30 day follow-up visit required for any subject who has ongoing AE or SAE at the time of his last study visit.

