7.3. Vital Signs and Physical Examination Findings

7.3.1. Definitions

The following vital signs parameters will be analyzed.

- Pulse (bpm)
- Systolic blood pressure, SBP (mmHg)
- Diastolic blood pressure, DBP (mmHg)

A listing of subjects with treatment-emergent clinically important vital signs will be presented, along with a listing of all vital sign measurements.

Table 5: Pulse, SBP and DBP are classified in the following abnormality codes.

	Pulse	DBP ^a	SBP ^a
Abnormality Code	(bpm)	(mmHg)	(mmHg)
Abnormally low	≤50	≤50	≤90
Grade 1 or mild	-	>90 - <100	>140 - <160
Grade 2 or moderate	-	≥100 - <110	≥ 160 - <180
Grade 3 or severe	-	≥110	≥180
Abnormally high	≥120	-	-

Classification of adverse events related to hypotension/hypertension should be done according to the DAIDS grading table (Appendix 7 at protocol).

In determining abnormalities, the following rules are applied:

- worst grades/abnormalities are determined over the whole observational period for each trial period separately, including post-reference scheduled *and* unscheduled measurements of that phase.
- The abnormalities 'abnormally low' and 'abnormally high'/grades are considered equally important, i.e. if a subject has as well an abnormally low as an abnormally high or graded value post-reference, both abnormalities are shown in the tables. (This means that the sum of the percentages can be more than 100%).

Definition treatment-emergent:

An abnormality will be considered treatment-emergent in a particular period if it is worse than the reference corresponding to this period. If the reference is missing, the abnormality is always considered as treatment-emergent. A shift from 'abnormally low' at reference to 'abnormally high' or 'grade' post reference (or vice versa) is also treatment-emergent.

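### SAP 2.2 puts the pre-dose Week 24 laboratory and vital-sign results of Delayed-arm participants who switch that same day into the D/C/F/TAF phase, in phase-based outputs only

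*SAP*

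**What the plan says.** SAP 2.2 defines two separate time structures.

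- **Visit windows (Table 2).** "The time intervals will be used for reporting of metabolic/weight, efficacy, and safety data". The Week 24 window is Day 127-182 in the Delayed arm and Day 127-210 in the Immediate arm.
- **Trial phases.** These are built for adverse events, for concomitant therapies, and "for the determination of the worst-case/toxicity/change in the cross-tabulations". For ongoing or completed subjects, the Phase I end date in the Delayed arm is "For delayed switched arm, use first D/C/F/TAF intake date" minus one day. In the other arm it is: "For immediate switch arm, use Week 24 visit date; if missing then" a projected date. Phase II begins at "Treatment Phase I end date +1" day.

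For vital signs, SAP 7.3.1 says that "worst grades/abnormalities are determined over the whole observational period for each trial period separately". It judges treatment-emergence against the reference belonging to the period concerned. No reference value is defined for Phase II. SAP 7.3.2 names only one reference for vital-sign changes, the time point nearest the first drug intake after randomization. SAP 2.7 likewise anchors Baseline to the start of the study.

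The Screening row of the phase table handles a same-day first dose by looking to what came last before that dose. The Phase I and Phase II rows have no such provision.

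Protocol 1.3 first dispenses D/C/F/TAF to the Delayed arm at Week 24. It schedules the metabolic profile, which carries the lipids, at Baseline, Week 24, Week 48 and early discontinuation only. On fasting it says: "If a participant has not fasted prior to the visit, the visit may proceed, but participant must return within 72 hours".

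**The concern.** Day minus one is a sensible boundary for an event whose onset falls on the day of the first new tablet. It does not suit a blood sample or blood pressure taken that morning before the tablet. At the Week 24 visit a Delayed-arm participant has had 24 weeks of randomized INI treatment, and the results measure that treatment. If the participant starts D/C/F/TAF the same day, the calendar rule files them under D/C/F/TAF. In the Immediate arm the Week 24 results stay in Phase I.

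Lipids are the most exposed, because Week 24 is their only scheduled post-baseline measurement in the first 24 weeks. Lipid abnormalities are one of the adverse-event groups of interest in SAP 7.1.1, cholesterol, LDL and triglycerides are DAIDS-graded, and Grade 3 and 4 laboratory abnormalities through Week 24 are a safety endpoint in Protocol 3.1. What is at stake is whether phase-based toxicity tables attribute on-treatment abnormalities to the right regimen.

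**Working it through.** **1. Reproduce the plan's own days (SAP Table 2).**
- Week 24 target: 24 × 7 + 1 = Day 169, as stated. The projected Week 24 date, first dose plus 7 × 24 days, is also Day 169 when the first dose is Day 1.
- Window limits by midpoints: (85 + 169)/2 = 127; (169 + 197)/2 = 183, so the Delayed window ends on Day 182; (169 + 253)/2 = 211, so the Immediate window ends on Day 210. All agree with Table 2.

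**2. Place a Week 24 sample drawn on Day 169.** Phase I end = visit day (Immediate) or first D/C/F/TAF day − 1 (Delayed). Phase II start = Phase I end + 1.

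| Arm | First D/C/F/TAF after Week 24 visit | Phase I ends | Phase II starts | Week 24 sample falls in |
|---|---|---|---|---|
| Immediate | not applicable | 169 | 170 | Phase I |
| Delayed | same day | 168 | 169 | **Phase II** |
| Delayed | 1 day later | 169 | 170 | Phase I |
| Delayed | 2 days later | 170 | 171 | Phase I |

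Only the same-day switcher is misplaced.

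**3. Count what Phase I keeps for a same-day switcher.**
- Lipids: scheduled post-baseline day 169; days up to 168: none, so 0 of 1. Phase II then holds the Week 24 (INI) and Week 48 (D/C/F/TAF) samples.
- Chemistry and vital signs: scheduled days 29, 85 and 169; days up to 168: 29 and 85, so 2 of 3.

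**4. Is the displaced result pre-dose?** The tablets are handed out at that visit, laboratory samples are drawn fasting, and the tablet must be taken with food (Protocol 1.3 and 6.1). A draw made at the visit would ordinarily precede a tablet taken the same day.

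**5. How many?** The documents neither fix nor report the day of first intake after Week 24. Target days 197 and 169 are 28 days apart, and the Week 28 visit is described as 4 weeks after the switch, so the plan expects switching at about the Week 24 visit. That does not give a same-day share. With 55 planned in the arm, the range is 0 to 55.

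**6. Fasting redraws.** A redraw may come up to 3 days after the visit: 169 + 3 = Day 172, still inside Day 127-182. If the participant has switched meanwhile, the phase rule correctly puts the redraw in Phase II, but the visit window can report it as the Delayed arm's Week 24 value.

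**7. After the fix.** With pre-dose results on the first-intake date kept in Phase I, the same-day switcher's counts become 1 of 1 for lipids and 3 of 3 for chemistry and vital signs, as for a next-day switcher.

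**The case against.** Much can be said for the plan, and most of it limits the point without removing it.

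- **The sample is not lost.** By-visit summaries use the windows, so a Day 169 lipid result is reported as Week 24. SAP 7.2.2 also plans a cross-tabulation of worst grade at Week 24, which on its natural reading is visit-based and shows the same result. This stands. A reader might infer that same-day switchers have no on-INI lipid data at all. They have the Baseline value as reference, and the Week 24 value in every by-visit output.
- **The through-Week-24 table could be programmed from windows.** SAP 7.2.2 uses visit language. But SAP 2.2 expressly assigns worst-toxicity cross-tabulations to phases, so the text leaves this open at best.
- **The Week 24 value could serve as the Phase II reference,** and then would not count as a post-switch abnormality. That would be sensible, but the SAP does not say it.
- **The consistency comparison is distorted.** A reader might infer this too. SAP 6.2.1.1 defines the Delayed arm's laboratory and blood-pressure changes from Week 24 to Week 48, so Week 24 is the starting value there, and the Grade 3-4 laboratory item is worded through Week 48 and not by phase. The documents do not support the inference for those items.
- **Different end rules by arm are not in themselves wrong.** Only one arm changes drug, and day minus one suits adverse events and concomitant therapies. This stands.
- **INI toxicity rates would be understated.** If a share *s* switches the same day and the denominator is all 55, a true lipid incidence *p* would show as *p*(1 − *s*). If only participants with a Phase I result are counted, and switching day is unrelated to lipids, it stays at *p* on fewer people. The SAP fixes neither *s* nor the denominator, so a lower percentage is not established.

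**Conclusion.** The point holds for phase-based outputs. As written, the rule assigns pre-dose, on-INI Week 24 laboratory and vital-sign results of same-day switchers to the D/C/F/TAF phase. Each such participant loses the only scheduled post-baseline lipid result and one of three chemistry and vital-sign visits from Phase I, and brings an INI result into Phase II. The Immediate arm has no corresponding loss.

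This rests on two things: that SAP 2.2's allocation of worst-grade tables to phases is followed literally, and that the same-day draw precedes the tablet. The number affected is anywhere from 0 to 55 of 55, and no change in an incidence can be calculated from the documents. The affected outputs are descriptive safety tables. The primary weight model, by-visit Week 24 summaries and Week 24-to-48 change comparisons do not use the phases and are not touched.

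**What to change.** In SAP 2.2, separate assessments from events at the Phase I/II boundary of the Delayed arm.

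- **Laboratory and vital-sign assessments:** results dated on or before the first D/C/F/TAF intake date, and taken pre-dose, belong to Phase I; later results belong to Phase II.
- **Phase II reference:** the last value on or before first D/C/F/TAF intake, stated once and applied in SAP 7.2.2 and 7.3.
- **Adverse-event onset and concomitant therapies:** keep intake date minus one day.
- **Fasting redraws:** flag Week 24 redraws taken after the first D/C/F/TAF dose, so that the Day 127-182 window does not report them as on-INI values.
- **SAP 7.2.2:** say whether the worst-grade table through Week 24 is built from phases or from windows.

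The cost is SAP wording and a programming change to date derivations. It needs no new data collection, and it mirrors the last-before-first-dose convention already used for Screening and Baseline.

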2.3. Pooling Algorithm for Analysis Centers

Not applicable.

2.4. Analysis Sets

2.4.1. All Subjects

All subject analysis set population includes subjects who were screened.

2.4.1.1. Intent-to-Treat Analysis Set

The intent-to-treat (ITT) analysis set will include all the subjects who were randomized and received at least 1 dose of treatment subsequent to randomization in the study. Subjects will be grouped according to the treatment arm (D/C/F/TAF FDC or Active-Control) to which they were randomized.

The ITT analysis set is the primary analysis set for primary endpoint (percent change in body weight) analysis. The ITT analysis set is also used for efficacy analysis. Efficacy data up to the last dose date of the randomized study treatment will be included.

2.4.1.2. Per-Protocol Analysis Set

Since an analysis on the ITT population may not be conservative in certain analysis settings, an analysis based on the per-protocol (PP) population will also be performed to investigate the impact of excluding subjects with major protocol violations and to evaluate the robustness of the primary and major secondary analysis results.

2.4.2. Safety Analysis Set

The safety analysis set includes all randomized subjects who received at least 1 dose of study intervention (i.e., ITT analysis set). The safety analysis (including all data collected up to 30-day follow-up visit) is also performed on the ITT analysis set. Participants will be assessed according to the actual intervention they received.

2.5. Definition of Subgroups

The pre-specified subgroups are summarized in the table below. Selected subgroup analyses will be performed for baseline and demographic characteristics tables. Additional subgroup analyses may be performed, if requested and deemed necessary.

Subgroup	Definition	
Race a*	Black/African American	
	Non-Black/African American	
Sex*	Female	
	Male	
Race:Sex*	Black/African American Female	
	Black/African American Male	

Subgroup	Definition
	Non-Black/African American
	Female
	Non-Black/African American Male
Ethnicity*	Hispanic or Latino
•	Non-Hispanic or Latino
	Others (Unknown/Not Reported)
Race/Ethnicity	Black/African American Hispanic or
	Latino
	Black/African American Non-
	Hispanic or Latino
	Non-Black/African American
	Hispanic or Latino
	Non-Black/African American Non-
	Hispanic or Latino
Baseline CD4+ categories	• >200
	• \leq 200
Age Group*	Adults
8	• 18-25
	• 26-50
	• 51-64
	 ≥65
BMI*	• normal 18 - <25 kg/m ²
	• overweight 25 - $<$ 30 kg/m ²
	• obese $\geq 30 \text{ kg/m}^2$
Waist circumference (inch)*	• Male WC ≥ 40"
, ,	• Males WC < 40"
	• Female WC ≥ 35"
	• Female WC < 35"
ARV Treatment Regimen at Time of Screening	BIC/FTC/TAF
	• DTG + FTC/TAF
	• RAL + FTC/TAF
	EVG/C/FTC/TAF
Delayed Switch Regimen	• DTG+FTC/TAF vs SYM
	BIC/FTC/TAF vs SYM
	• RAL+FTC/TAF vs SYM
	EVG/C/FTC/TAF vs SYM
Presence of one or more primary and/or DRV Resistance-Associated Mutation (RAMs),	Yes/No
` '	
Presence of one or more NRTI RAMs	Yes/No
Presence of one or more NNRTI RAMs	Yes/No
Presence of one or more Primary INI RAMs	• Yes/No
Presence of one or more Secondary INI RAMs	• Yes/No
HIV Acquisition Risk Factor b*	Heterosexual contact
_	• MSM
	• Others

Subgroup	Definition
NAFLD fibrosis score*	F0-F2IndeterminateF3-F4
HAIR scores *	• >=2 • <2
Baseline Co-morbid conditions (defined by Medical History)	Diabetes Y/NHTN Y/NHyperlipidemia Y/N

^a Non-Black/African American=White, American Indian or Alaska Native, Asian, Native Hawaiian or other Pacific Islander, Multiple, Other, Unknown, and Not reported.

2.6. Study Day and Relative Day

Study Day 1 or Day 1 refers to the start of the first study agent administration or randomization date. If subjects start medication a day after baseline/screening visit, actual treatment administration date will be used as Day 1 instead of screening/baseline visit date.

All metabolic, efficacy and safety assessments at all visits will be assigned a day relative to this date.

2.7. Baseline and Endpoint

Baseline is defined as the last observation prior to the start of the first study agent administration or randomization date.

Endpoint is defined as the last available postbaseline result within the analysis period. Unscheduled visit results are included in this definition and will be considered as the endpoint value if the unscheduled visit result is the last postbaseline result available within the analysis period.

2.8. Imputation Rules for Missing AE Date of Onset/Resolution

Partial AE onset dates will be imputed as follows:

- If the onset date of an adverse event is missing day only, it will be set to:
 - First day of the month that the AE occurred, if month/year of the onset of AE is different than the month/year of the study treatment start.
 - The day of the study treatment start, if the month/year of the onset of AE is the same as month/year of the study treatment start and month/year of the AE resolution date is different
 - The day of the study treatment start or day of AE resolution date, whichever is earliest, if month/year of the onset of AE and month/year of the study treatment start and month/year of the AE resolution date are same
- If the onset date of an adverse event is missing both day and month, it will be set to the earliest of:

^b Others= Intravenously injectable drug use, Blood transfusion, Hemophilia-associated injections, Occupational exposure, Mother to child transmission and other.

^{*} Subgroup analyses will be performed for these subgroups only

- January 1 of the year of onset, as long as this date is on or after the study treatment start date
- Month and day of the study treatment start date, if this date is the same year that the AE occurred
- Last day of the year if the year of the AE onset is prior to the year of the study treatment start date,
- The AE resolution date.
- Completely missing onset dates will not be imputed.

Partial AE resolution dates not marked as ongoing will be imputed as follows:

- If the resolution date of an adverse event is missing day only, it will be set to the earliest of the last day of the month of occurrence of resolution or the day of the date of death, if the death occurred in that month.
- If the resolution date of an adverse event is missing both day and month, it will be set to the earliest of December 31 of the year or the day and month of the date of death, if the death occurred in that year.
- Completely missing resolution dates will not be imputed.

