For the most comprehensive non-clinical and clinical information regarding D/C/F/TAF FDC, refer to the Investigators Brochure.¹⁹ For further information on the INI + TAF/FTC ARV regimens, please refer to ARV-specific Prescribing Information.

The term "study intervention" throughout the protocol, refers to D/C/F/TAF FDC and INI + TAF/FTC ARV regimen; otherwise, the individual study intervention names are used.

The term "sponsor" used throughout this document refers to the entities listed in the Contact Information page(s), which will be provided as a separate document.

The term "participant" throughout the protocol refers to the common term "subject".

25

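### SAP 2.8 imputes partial AE onset dates without reference to the Delayed arm's switch, so unknown-day events in the switch month fall in the INI phase unless the switch was on the 1st

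*SAP*

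**What the plan says.** **Imputation (SAP 2.8).**
- When only the onset day is missing, the date becomes "First day of the month that the AE occurred, if month/year of the onset of AE is different". The comparison is with one date: the rule applies when the onset month "is different than the month/year of the study treatment start".
- In the treatment-start month the rule differs: "The day of the study treatment start, if the month/year of the onset of AE is the same" and the event resolved in another month. If it resolved in that same month, the earlier of the start day and the resolution date is used.
- When day and month are both missing, the earliest of several candidates is taken. These include 1 January of the onset year, the treatment start date and the resolution date. None refers to the switch.

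**Meaning of the anchor.** SAP 2.8 does not define study treatment start. The nearest definition is in SAP 2.6: "Study Day 1 or Day 1 refers to the start of the first study agent administration or randomization date". Protocol Section 2 says that study intervention "refers to D/C/F/TAF FDC and INI + TAF/FTC ARV regimen", so in the Delayed arm it begins with the continued INI regimen. SAP 7.1.2 also judges partial dates against the first administration of study drug.

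**Phases (SAP 2.2).** "Phases will be constructed for each subject as follows for adverse events". For the end of Treatment Phase I the table says "For delayed switched arm, use first D/C/F/TAF intake date", less one day. Treatment Phase II begins at "Treatment Phase I end date +1" day, which in the Delayed arm is the first D/C/F/TAF intake.

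**Attribution (SAP 2.4.2).** Safety is assessed by the intervention actually received.

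**The concern.** The Delayed arm has two treatment starts that matter for safety: Day 1 on the INI regimen and the switch to D/C/F/TAF. SAP 2.8 keeps a partial date from falling before the first of these but does nothing at the second. Events that began shortly after the switch can therefore be dated before it and counted under the regimen the participant had already left.

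Two outputs are exposed. The first is any AE table split by treatment phase. The second is the comparison of the Immediate arm's first 24 weeks on D/C/F/TAF with the Delayed arm's 24 weeks on D/C/F/TAF (Protocol 3.3, SAP 6.2.1.1). There the two arms' D/C/F/TAF start months would be handled in opposite ways, which can lower the Delayed arm's D/C/F/TAF event counts relative to the Immediate arm's.

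**Working it through.** The plan gives no figure on this point, so there is none to reproduce. The check applies the SAP 2.8 rule to the SAP 2.2 phase boundaries.

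**Assumptions.** Study treatment start is Day 1. The switch is at Day 1 + 168 days (24 × 7). True onset is uniform over the days of the switch month.

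**1. Which bullet applies?** The switch is 168 days after Day 1, or 161 days if the visit falls 7 days early. Either exceeds any calendar month. Over 365 consecutive Day 1 dates from 1 January 2021, the switch month equalled the start month 0 times. The first-of-month bullet therefore always applies.

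**2. Which phase does the imputed date fall in?** Phase I ends at switch date − 1, so an onset on the 1st is in Phase I unless the switch is itself on the 1st. In the 365-date run the imputed onset fell in Phase I for 353 dates: 353/365 = 96.7%. The other 12 (12/365 = 3.3%) are switches on the 1st.

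**3. How many of these events truly began on D/C/F/TAF?** For a month of L days and a switch on day s, the share of onset days on or after the switch is (L − s + 1)/L. Averaged over s this is (L + 1)/(2L); with L = 30, 31/60 = 51.7%. The 365-date run gives 51.6%.

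**4. How many of those are counted under INI?** All except those in months where s = 1: 1 − 2/(L + 1). With L = 30, 1 − 2/31 = 93.5%. The run gives 93.6%. The share of true pre-switch onsets moved to D/C/F/TAF is 0%, so the error runs one way.

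**5. Overall share misplaced.** 0.516 × 0.936 = 0.483, or about 48% of unknown-day events in the switch month. The remaining 52% or so are placed correctly.

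**Example.** Day 1 = 27 September 2021 gives a switch on 14 March 2022. An event dated March 2022 becomes 1 March 2022 and falls in Phase I (INI). In that month 31 − 14 + 1 = 18 of 31 days (58%) are on or after the switch.

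**6. The Immediate arm's equivalent month.** D/C/F/TAF starts at Day 1, so an unknown-day event in that month is set to the start day and counted on D/C/F/TAF, unless it resolved earlier in the same month.

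**7. Onsets with only a year.** If the onset year is the year of the switch, the date becomes the treatment start date (Day 1 in the same year) or 1 January (Day 1 in the year before), or the resolution date if earlier. The first two precede the switch unless it fell on 1 January. The gap is the same.

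**8. Does anything else repair it?** SAP 7.1.2 decides whether a partial-date event is treatment-emergent relative to the first administration. It does not decide the phase.

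**The case against.** **The effect is probably very small.** This stands. AEs are collected at Week 24 and again at Week 28, a visit added for the Delayed arm, so recall intervals around the switch are short and dates can be queried. AE and consistency analyses are descriptive, with no formal testing. The documents give no count of partial dates.

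**The anchor may mean something else.** Reading study treatment start as Day 1 is an inference, though SAP 2.6, SAP 7.1.2 and Protocol Section 2 all point that way. If the sponsor meant the first D/C/F/TAF intake for the Delayed arm, SAP 2.8 has to say so. A text change is needed either way.

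**The consistency comparison may not depend on phase.** This stands in part. Protocol 3.3 and the heading of SAP 6.2.1.1 give the Delayed window as Week 24 to Week 48. The AE items listed under that heading compare events through Week 24 (Immediate) with events through Week 48 (Delayed). Read literally, those items count the event in whichever phase it falls. A bias in this comparison follows only if the Week 24 to 48 window is the one intended.

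**Events may cluster after a switch.** A reader might infer that well over half of the switch-month events belong to D/C/F/TAF, because Protocol 4.2 reports 543 of 625 AEs in the first 24 weeks of an earlier switch study. That figure compares two 24-week halves of another trial. It says nothing about how onsets are spread within one calendar month, so it cannot raise the estimate.

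**The remedy errs the other way.** This is correct. Anchoring to the switch moves true INI onsets into D/C/F/TAF. About 48% of switch-month days precede the switch (100% − 51.6%), so before the resolution-date cap the share misplaced is about the same as now. What changes is the direction and the consistency between arms.

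**Conclusion.** The point holds as a low-priority correction. On the natural reading of the SAP, an unknown-day AE in the Delayed arm's switch month goes to the INI phase for about 97% of switch dates. Under uniform onset about half of these events began on D/C/F/TAF, and nearly all of those are counted under INI. This works against attribution by actual intervention (SAP 2.4.2) and against the convention applied at the Immediate arm's D/C/F/TAF start.

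A reader might infer that every such event is misplaced. That is not supported: a switch on the 1st is an exception, and roughly half of the events truly began on INI and are placed correctly. Nor do the documents support calling the effect material, since the number of partial dates is unknown and probably small. The by-phase AE tables are affected; the consistency comparison is affected only under the Week 24 to 48 reading; the primary endpoint is not affected. The percentages rest on a switch at 168 days, uniform onset within the month, and Day 1 as the anchor.

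**What to change.** Add to SAP 2.8, for the Delayed arm: if the known part of a partial onset date (month and year, or year only) matches that of the first D/C/F/TAF intake and is compatible with onset on or after it, set onset to that intake date, or to the resolution date if earlier. Define study treatment start in the same section.

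State the downside beside the rule: it errs towards D/C/F/TAF. That is the conservative direction for the study drug and matches the convention already used at treatment start. For year-only dates the uncertain period is longer, and the 48% figure does not apply to them. Reporting how many events the rule touched would let a reader judge its effect.

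The AE items in SAP 6.2.1.1 should also state whether the Delayed window starts at Week 24.

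Cost: one rule in the SAP and one condition in the AE program, with no new data.
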